6.12.12.2.1. Analyses of Characteristics of ADA Immune Response

The analyses of ADA effects will be conducted on all evaluable patients within the defined Safety Population, OLE Period Population, and LTE Safety Population.

The overall frequency and percentage (incidence) of patients will be summarized for the TE-ADA status groups and the time-varying TE-ADA status groups. Scheduled visits, unscheduled visits, and repeat measurements will be included.

In addition, the overall frequency and percentage (incidence) of patients will be summarized for the patients who are baseline ADA positive by TE-ADA status groups. For those patients who are TE-ADA positive, a summary of titer values and the proportion of patients who are NAb positive will also be provided.

The time to the development of TE-ADAs (TE-ADA positive, low titer, moderate titer, high titer, and NAb positive) will be calculated as follows:

$$\text{Time to development of TE-ADAs/NAb (in weeks)} = (\text{Date of development of TE-ADAs/NAb} - \text{Date of first injection of study treatment} + 1) / 7.$$

If a patient has not developed TE-ADAs/NAbs, he/she will be censored at the date of the last immunogenicity assessment. If a patient does not have any postbaseline assessments for immunogenicity, he/she will be censored at the date of randomization.

For each TE-ADA status dichotomous variable (as defined in [Table RHCG.6.17](#)), summaries will be provided of the total postbaseline time in the greater-TE-ADA status for patients who were at some point postbaseline in the greater-TE-ADA status group. Postbaseline time in greater-TE-ADA status for each patient will be aggregated.

A by-patient listing to include treatment, visit date, visit, ADA result, TE-ADA result, NAb result, ADA titer value, ixekizumab concentration, and ADA and NAb inconclusive results will also be provided, for patients with any one sample of ADA (or NAb) positive or inconclusive.

6.12.12.2.2. Analyses of Treatment-Emergent ADA Effects on Efficacy

Efficacy analyses for the OLT (Safety Population) and OLE (OLE Period Populations) Periods will be conducted on all evaluable patients.

Assessment of JIA ACR 30 at Weeks 16 and 104 with NRI will be summarized by the TE-ADA and TE-ADA positive status groups, as described in Section [6.12.12.2.1](#) for the Safety and OLE Period Populations, respectively.

6.12.12.2.3. Analyses of Treatment-Emergent ADA on Specific Adverse Events

The analyses of TE-ADA effects on safety will be conducted on all immunogenicity evaluable patients for the OLT (Safety Population), OLE (OLE Period Population), and LTE (LTE Safety Population) Periods when patients are on ixekizumab, including switch to ixekizumab.

Adverse events of special interest of allergic reaction/hypersensitivity (anaphylaxis and non-anaphylaxis) and of injection-site reactions will be included in an assessment of AE to TE-ADA over time. Timing of an AE will be taken to be the reported AE start date.

For each TE-ADA status dichotomous variable (as defined in [Table RHCG.6.17](#)), patients will be categorized according to whether they were (i) always in lesser-TE-ADA status postbaseline or (ii) at some point postbaseline, were in greater-TE-ADA status. For each AESI, within the time-varying TE-ADA status groups, a summary will be provided of the number of patients who had no event, events only while in lesser-TE-ADA status for group (i), or – for group (ii) – at least 1 event while in greater-TE-ADA status.

Additionally, summaries will be provided of the total number of AESI events (with unique start dates) by time-varying TE-ADA status groups at the event date. The summaries will aggregate time respectively in greater-TE-ADA status and in lesser-TE-ADA status, along with the event rates (rates per 100 patient-years) relative to those aggregate times.

By-patient listings will be provided for patients with TE-ADA who experience a treatment-emergent allergic reaction/hypersensitivity reaction or an injection site reaction. A listing of immunogenicity results will also be provided.

6.13. Subgroup Analyses

The descriptive statistical analysis will be conducted for the following subsets of patients at each post-baseline visit for the OLT (ITT Population), and the OLE (OLE and Switcher Populations) Periods. Subgroups from [Table RHCG.6.2](#) will be analyzed for JIA ACR30/50/70/90/100.

Additional subgroup analyses on efficacy may be performed as deemed appropriate and necessary.

6.14. Protocol Violations

Protocol deviations will be tracked by the clinical team, and their importance will be assessed by key team members during protocol deviation review meetings.

Potential examples of deviations include patients who receive excluded concomitant therapy, significant noncompliance with study medication (<80% of assigned doses taken, failure to take study medication, and taking incorrect study medication), patients incorrectly enrolled in the study, and patients whose data are questionable due to significant site quality or compliance issues. Refer to the Trial Issue Management Plan (TIMP) for the stat-identified important protocol deviations (IPDs).

The number and percentage of patients having IPD(s) will be summarized in the OLT and OLE Periods (by treatment) within category and subcategory of deviation using the ITT, OLE, and Switcher populations, respectively. Individual patient listings of IPDs will be provided.

6.15. Interim Analyses and Data Monitoring

An interim analysis will be conducted under the auspices of a DMC according to the specifications set forth in the protocol.

An interim analysis will be performed to determine if the study should be stopped for futility when 40 evaluable ixekizumab-treated patients have completed the OLT period, i.e. completed Week 16 (Visit 7) or “early terminated between Weeks 0 and 16” or “discontinued between Weeks 0 and 16.” If the Week 16 JIA ACR30 response rate (subject to NRI imputation as appropriate) is less than 40% at interim, futility will be declared, and the study will be terminated, after the applicable required regulatory agreements are obtained.

An interim analysis may be performed at the time (that is, a cut-off date) the last patient completes the OLT period.

A DMC will oversee the conduct of Study RHCG. The DMC will consist of members external to Lilly with the exception of the LRL Senior Management Designee. This DMC will follow the rules defined in the DMC charter, focusing on potential and identified risks for this molecule and for this class of compounds. The DMC will review and evaluate planned interim analyses.

Data that the DMC will review include, but is not limited to, study discontinuation data, summary of reasons for missing JIA ACR30 data at Week 16, AEs including SAEs, PK data, clinical laboratory data, vital signs data, and growth. The DMC may recommend continuation of the study as designed, temporary suspension of enrollment, or discontinuation of a particular dose regimen or discontinuation of the entire study. The DMC may request to review efficacy data to investigate the benefit/risk relationship in the context of safety observations for ongoing patients in the study. Details of the DMC and interim safety analyses will be documented in a DMC charter and DMC analysis plan.

6.15.1. *Interim Analysis Plan*

Analyses for the DMC will include listings and/or summaries of the following information:

- patient disposition, demographics, and baseline characteristics
- exposure
- adverse events, to include the following:
 - treatment-emergent adverse events
 - serious adverse events, including deaths
 - selected special safety topics
- clinical laboratory results
- vital signs
- growth parameters (for example, height, weight, assessment of bone age)

All listings will include patient ID. Summaries will include TEAEs, SAEs, special topics AEs, and treatment-emergent high and low laboratory and vital signs in terms of counts, percentages and incidence rates, where applicable. For continuous analyses, box plots of laboratory analytes will be provided by time point.

The DMC will request efficacy data to confirm a reasonable benefit/risk profile for ongoing patients in the studies. Further details are given in the DMC charter.

In order to mitigate the effects of potentially slow enrollment, and in order to avoid unnecessary exposure of pediatric patients to treatment, Study RHCG will conduct automated continual learning (ACL) if the study continues beyond the futility interim at 40 evaluable ixekizumab-treated patients. After the interim, the sponsor will conduct periodic ACL snapshots of the raw data to determine if it will still be possible to meet the efficacy critical success factor (CSF) at the study's conclusion. By construction, Study RHCG will meet the efficacy CSF if and only if there are fewer than 37 ixekizumab nonresponders at the end of the study (subject to NRI imputation as appropriate). If an ACL snapshot records fewer than 37 ixekizumab nonresponders, then it is still possible to meet the CSF, and the study will continue. However, if the number of ixekizumab nonresponders in an ACL snapshot is at least 37, then there will be 43 or fewer ixekizumab

responders at the end of the study, which is not enough responders to meet the CSF success in the final analysis. For this reason, if an ACL snapshot reports at least 37 nonresponders, then the sponsor will conduct an additional futility interim.

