10.1. Sample Size Determination

The Bayesian methodology results in a posterior distribution which rigorously quantifies the uncertainty around the estimate of the JIA ACR 30 response. The primary objective of this study is to detect a JIA ACR 30 response rate of at least 50% for ixekizumab-treated participants at Week 16.

A sample size of at least 80 participants assigned to ixekizumab has been shown via simulation to have reasonable operating characteristics as follows:

- a study success rate greater than 80% if the true JIA ACR 30 response is at 60%
- a false-positive rate of less than 1% if the true JIA ACR 30 response is placebo-like at 35%

These rates are derived from the Bayesian decision criterion, but are similar to a traditional power calculation.

Overall, approximately 100 participants will be assigned to therapy in this study.

Of the 80 ixekizumab-treated participants in this study, 20 bDMARD-naive participants will be randomized to ixekizumab. An additional 20 participants will be randomized to adalimumab (1:1 randomization to ixekizumab or adalimumab). The remaining 60 participants who are either bDMARD-naive or bDMARD-IR will be assigned to ixekizumab in the OLT period.

The above sample size and power estimates are based on Fixed and Adaptive Clinical Trials Simulator version 6.0 (FACTS™).

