6.9. Efficacy Analyses

6.9.1. Primary Outcome and Methodology

The analysis methods and analysis periods are described in [Table RHCG.6.5](#) and [Table RHCG.6.6](#).

The primary efficacy endpoint is the percentage of ixekizumab-treated patients meeting JIA ACR30 response criteria at Week 16. A JIA ACR30 response is defined as at least 30% improvement from baseline in at least 3 of any 6 variables in the core set, with no more than 1 of the remaining variables worsening by >30%.

The individual components that make up the JIA ACR30 core set variables are defined as follows:

- Number of active joints in 73 joints (active joint defined as a joint that is swollen, or in the absence of swelling, has loss of passive motion accompanied by either pain on motion or joint tenderness)
- Number of joints with limited range of motion in 69 joints
- Physician's Global Assessment of Disease Activity (21-circle Visual Analogue Scale [VAS])
- Parent's Global Assessment of Well-Being
- Physical function as assessed by the Childhood Health Assessment Questionnaire (CHAQ)
- Erythrocyte sedimentation rate (ESR)

A listing of the primary efficacy endpoint will be provided.

If the study is not stopped for futility, the posterior probability of the Week 16 JIA ACR30 response rate exceeding 50% will be calculated, and the study objective will be successfully met (i.e., a positive study) if this posterior probability is at least 80%.

The beta-binomial 2-stage Bayesian model will be used for the primary analysis. The beta shape parameters are:

- a : the degree of response
- b : the magnitude of non-response

The prior distribution of the JIA ACR30 response rate at Week 16, p , is:

$$p \sim \text{beta}(a, b)$$

where a and b are the prior parameters and have an intuitive interpretation of prior responders and non-responders, respectively. The prior will be pre-specified with parameters $a = b = 1/2$, which is largely accepted as a Jeffery prior.

Let $X_i|p$ be the JIA ACR30 response at Week 16 of the i^{th} patient treated with ixekizumab. X_i conditionally follows a Bernoulli distribution:

$$X_i|p \sim \text{Bernoulli}(p).$$

The number of JIA ACR30 responders at Week 16, K is binomial:

$$K|p \sim \text{binomial}(n, p)$$

where n is the sample size of the ixekizumab patients of the ITT population in the study.

Due to conjugacy in the beta-binomial model, the posterior distribution of p is:

$$p|k \sim \text{beta}(a + k, b + n - k)$$

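### The 37-non-responder trigger in SAP 6.15.1 is exact only at a final ixekizumab n of 80 or 81, and the section does not state that condition

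*SAP*

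**What the plan says.** SAP 6.15.1 (Interim Analysis Plan) describes snapshots of the data, called automated continual learning (ACL), that follow the futility look at 40 ixekizumab participants. Their stated purposes begin "In order to mitigate the effects of potentially slow enrollment" and include sparing children unnecessary exposure. The section says "the sponsor will conduct periodic ACL snapshots of the raw data" to see whether the efficacy critical success factor (CSF) can still be met. The rule is that "Study RHCG will meet the efficacy CSF if and only if there are fewer than 37 ixekizumab nonresponders at the end of the study". Below that count, "If an ACL snapshot records fewer than 37 ixekizumab nonresponders, then it is still possible to meet the CSF, and the study will continue". At 37 or more, "then there will be 43 or fewer ixekizumab" responders at the end, which the SAP says is too few, and so "the sponsor will conduct an additional futility interim".

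SAP 6.9.1 does not fix n for the primary analysis: n "is the sample size of the ixekizumab patients of the ITT population in the study". Protocol 10.1 treats 80 as a minimum: "A sample size of at least 80 participants assigned to ixekizumab has been shown via simulation to have reasonable operating characteristics". SAP 5.2 repeats this. Protocol 7.2 gives at least 20 participants randomised to ixekizumab and approximately 60 assigned to it without randomisation.

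**The concern.** The rule is worded as an equivalence with no condition on n, yet the number of non-responders compatible with success depends on the final ixekizumab n. If that n differs from 80, the snapshot rule and the primary analysis can disagree.

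- With a larger arm, the sponsor could call an additional futility interim on the stated premise that success is out of reach when it is not.
- With a smaller arm, the sponsor could be told that success is still possible when it is not. That works against the aim of limiting exposure.

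**Working it through.** **Inputs.** The prior is Beta(0.5, 0.5) (Protocol 10.3.3.1, SAP 6.9.1). Success is a posterior probability of at least 0.80 that the response rate exceeds 0.5 (same sections). The analysis n is the actual ixekizumab ITT count (SAP 6.9.1).

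**Formula.** With k responders among n, the posterior is Beta(0.5 + k, 0.5 + n − k), and P(p > 0.5) is its upper tail at 0.5. Let k*(n) be the smallest k for which this is at least 0.80. Success becomes impossible once the non-responder count reaches n − k*(n) + 1.

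**The plan's own figure, n=80.**
- 44 responders, 36 non-responders: 0.814, success.
- 43 responders, 37 non-responders: 0.749, failure.

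So k*(80) = 44 and the trigger is 80 − 44 + 1 = 37, as the SAP says. Requiring 44 of 80 gives a success probability of 0.848 at a true rate of 60% and 0.0002 at 35%. These agree with the stated figures of above 80% and below 1%.

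**Other sizes.**

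| Final n | k*(n) | Posterior at k*(n) | Posterior at k*(n) − 1 | Correct trigger |
|---|---|---|---|---|
| 76 | 42 | 0.821 | 0.754 | 35 |
| 78 | 43 | 0.817 | 0.751 | 36 |
| 79 | 44 | 0.844 | 0.784 | 36 |
| 80 | 44 | 0.814 | 0.749 | 37 |
| 81 | 45 | 0.841 | 0.782 | 37 |
| 82 | 45 | 0.811 | 0.746 | 38 |
| 84 | 46 | 0.809 | 0.744 | 39 |

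- n=81: 37 is still the right trigger. The responder bound becomes 81 − 37 = 44, so the figure 43 already fails to match, without consequence.
- n=82: 37 non-responders leave 45 responders, posterior 0.811. This is a success that the SAP excludes.
- n=79: 36 non-responders leave 43 responders, posterior 0.784. This is a failure that the SAP calls still possible.

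**How often, if a size is assumed.** The documents give no probability for any final n. The figures below are conditional on the n shown and on a true response rate of 60%.

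- n=82: success with 37 or more non-responders means exactly 45 responders. The binomial probability is 5.7%.
- n=84: 46 or 47 responders, 5.4% + 6.6% = 12.0%.
- n=79: failure with fewer than 37 non-responders means exactly 36 non-responders, 5.4%.

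The figures for n=82 and n=84 are upper bounds on false triggers, because a snapshot must also fall while outcomes are outstanding. If the non-responder that reaches the count is the last outcome, nothing is left to misjudge. Taking outcomes as arriving in random order and removing that case:

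- n=82: 5.7% × 45/82 = 3.1%.
- n=84: 5.4% + 6.6% × 47/84 = 9.1%. With 46 responders there are 38 non-responders, so the 37th is never last.
- n=79: 5.4% × 43/79 = about 3.0%.

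**The case against.** The strongest reply is that nothing has been miscalculated and that the planning size is not hidden. The numbers 37 and 43 sum to 80. SAP 5.2 gives 20 randomised plus 60 assigned to ixekizumab. The SAS example in SAP 6.9.1 uses 80. All of this stands: a careful reader can recover n=80, and at that size the rule is exact. What remains is that a rule worded as an equivalence and applied to live data should carry its condition, because the same documents treat 80 as a minimum and the non-randomised group as approximate.

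A second reply is that a shortfall is poorly supported. That is largely fair. Slow enrolment is not the same as under-enrolment. Dropout does not reduce n either, because non-responder imputation keeps ITT participants who discontinue as non-responders. The n=79 case therefore needs fewer participants to be assigned than planned.

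A third reply is that holding 80 during enrolment, as proposed below, leaves the rule unchanged for most of the time it operates. This is also true. A trigger that fires before enrolment closes would still fire, and the fix has to say what such a trigger means.

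A reader might infer that the SAP contains an arithmetic error, or that the trial could be stopped wrongly by this rule alone. The documents support neither. Both figures are right at n=80, and reaching 37 leads to a further futility interim, not to an automatic stop.

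**Conclusion.** The point holds as an unstated condition on a decision threshold, with minor impact. The trigger of 37 matches the primary analysis only at a final ixekizumab ITT n of 80 or 81. It is too strict from 82 upward, a size that a planned minimum permits, and too lenient at 79 and below, which requires a shortfall in enrolment.

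The posteriors rest only on the documents' prior, success criterion and definition of n. The percentages also rest on an assumed final n and a true rate of 60%. They should not be read as the chance that this trial goes wrong.

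It would be tempting to conclude that the trial's success criterion is affected. It is not, because SAP 6.9.1 applies the posterior to the actual n whatever the snapshots showed.

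**What to change.** In SAP 6.15.1:

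1. State that 37 and 43 assume a final ixekizumab ITT n of 80.
2. Define the trigger as n − k*(n) + 1, where k*(n) is the smallest responder count with a posterior probability of at least 0.80. Use the planned n of 80 during enrolment and the actual number assigned to ixekizumab once enrolment closes.
3. Add the look-up table:

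| Final ixekizumab n | Trigger (non-responders) |
|---|---|
| 76–77 | 35 |
| 78–79 | 36 |
| 80–81 | 37 |
| 82–83 | 38 |
| 84–85 | 39 |
| 86–87 | 40 |
| 88–89 | 41 |
| 90–92 | 42 |

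4. Replace the responder bound of 43 with fewer than k*(n).
5. Say that a trigger fired before enrolment closes is conditional on n=80, and that the additional futility interim recomputes it at the n then expected.

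The cost is one revised paragraph and a short table. No participants are added and the success criterion does not change.

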6.16. Annual Report Analyses

Annual report analyses, such as for the Development Update Safety Report (DSUR), will be documented in a separate document.

6.17. Clinical Trial Registry Analyses

Additional analyses will be performed for the purpose of fulfilling the Clinical Trial Registry (CTR) requirements.

Analyses provided for the CTR requirements include the following:

Summary of adverse events, provided as a dataset which will be converted to an XML file. Both Serious Adverse Events and 'Other' Adverse Events are summarized: by treatment group, by MedDRA preferred term.

- An AE is considered 'Serious' whether or not it is a TEAE.
- An AE is considered in the 'Other' category if it is both a TEAE and is not serious. For each Serious AE and 'Other' AE, for each term and treatment group, the following are provided:
 - the number of participants at risk of an event
 - the number of participants who experienced each event term
 - the number of events experienced.
- Consistent with www.ClinicalTrials.gov requirements, 'Other' AEs that occur in fewer than 5% of patients/subjects in every treatment group may not be included if a 5% threshold is chosen (5% is the minimum threshold).
- AE reporting is consistent with other document disclosures for example, the CSR, manuscripts, and so forth.

7. References

[CDC] Centers for Disease Control and Prevention resources page. National Center for Health Statistics. Data table of weight-for-age charts. 2019. Accessed October 20, 2016. http://www.cdc.gov/growthcharts/html_charts/wtage.htm

[CDC] Centers for Disease Control and Prevention resources page. A SAS program for the 2000 CDC growth charts that includes the extended BMI calculations. Updated January 9, 2023. Accessed March 15, 2023. <https://www.cdc.gov/nccdphp/dnpao/growthcharts/resources/sas.htm>

[EMA] European Medicines Agency. ICH E9 (R1) Addendum on estimands and sensitivity analysis in clinical trials to the guideline on statistical principles for clinical trials. 2020. Accessed December 14, 2020. <https://www.ema.europa.eu/en/ich-e9-statistical-principles-clinical-trials>

Appendix 1. Algorithm for Determining JIA ACRx Response

Details presented in this appendix will use “ x ” as a generic symbol, and the appropriate number (either 30, 50, 70, 90, or 100) is to be filled in when implementing in dataset programming code.

Juvenile idiopathic arthritis (JIA) American College of Rheumatology (ACR) x response is defined as at least $x\%$ improvement from baseline in at least 3 of any 6 variables in the core set, with no more than 1 of the remaining variables worsening by more than 30% from baseline.

- active joint count
- limited range of motion joint count
- physician global assessment of disease activity
- parent’s global assessment of well-being
- physical function as measured by Childhood Health Assessment Questionnaire (CHAQ), and
- erythrocyte sedimentation rate (ESR).

% change from baseline at a visit is calculated as:

$$(\text{value at visit} - \text{baseline value}) * 100 / \text{baseline value}$$

Change at a visit is calculated as:

$$\text{value at visit} - \text{baseline value}$$

The following abbreviations will be used throughout this appendix to refer to the items needed in the algorithm definitions:

Parameter	Abbreviation for the Parameter
% change from baseline in active joint count	AJ73
% change from baseline in limited range of motion joint count	LOM69
% change from baseline in parent’s global assessment of well-being	PGAWB
% change from baseline in physician’s global assessment of disease activity	PHYGA
% change from baseline in physical function as measured by Childhood Health Assessment Questionnaire (CHAQ)	CHAQ
% change from baseline in erythrocyte sedimentation rate (ESR)	ESR
Value of erythrocyte sedimentation rate	esr

Note:

- An *esr* value is within normal range if it is ≤ 20 .
- If the *esr* is elevated (*esr* > 20) due to JIA, then *esr* is used for calculation.
- If the *esr* is elevated due to a reason other than JIA, then *esr* is not used for calculation.
- If both baseline and postbaseline value of *esr* is within normal range (≤ 20), then the percent change of *esr* is set at 0 (no change).

JIA ACR30 Response Calculation

Two-step calculation; first step calculates worsening, and second step calculates improvement.

Step 1: Worsening (the increase in the score is worsening):

Check $> 30\%$ worsening. Specifically check if percent change from baseline is more than 30%, i.e.,

$$\text{If } (\text{parameter} > 30\%) = 1, \text{ else } 0$$

Count how many variables have more than 30% worsening; if the worsening count is 2 or more, conclude that the patient is a nonresponder. If the worsening count is 1 or less, proceed to Step 2.

Step 2: Improvement (count):

Check $\geq 30\%$ improvement. Specifically, check if percent change from baseline is less than or equal to -30% , i.e.,

$$\text{If } (\text{parameter} \leq -30\%) = 1, \text{ else } 0$$

Count how many variables have at least 30% improvement; if the count is 3 or more, conclude that the patient is a responder; if count is 2 or less, conclude that the patient is a nonresponder.

Note:

Scenario 1: If no variable is missing, proceed as described in Step 1 and/or Step 2, whichever applies.

Scenario 2: If there are variables missing at post-baseline, apply last observation carried forward (LOCF) first at component level, then back to Scenario 1 (LOCF cannot be applied across study periods, and the patient needs to have at least 1 post-baseline visit to apply LOCF. The baseline value cannot be carried forward).

Note for ESR : If the *esr* at a particular visit is missing, then the last observation is carried forward for the visit. However, for the LOCF visit, if the elevation is attributable to a medical condition other than the study condition as well, then the *esr* value at the current visit is treated as missing.

Scenario 3: If there are variables missing at baseline, use nonmissing components as the core sets, then back to Scenario 1. Unless specified otherwise, if there are variables with baseline value = 0, all postbaseline percent improvement is not calculable; hence, consider these variables as missing and use nonmissing components as core sets, then back to Scenario 1.

Note: for Scenario 3:

- If 1 component is missing, the remaining 5 components will be used as core set. If 3 out of 5 components are improving and no more than 1 out of 5 is worsening, the patient will be considered as a responder.
- If 2 components are missing, the remaining 4 components will be used as core set. If 3 out of 4 components are improving and no more than 1 out of 4 is worsening, the patient will be considered as a responder.
- If 3 components are missing, the remaining 3 components will be used as core set. If all 3 components are improving, the patient will be considered as a responder.
- If more than 3 components are missing, there will not be sufficient information; thus, the patient will be considered as a nonresponder.

